The primary aim of this study is to determine the energy intake-independent effects of leptin on energy metabolism in lipodystrophic subjects. Important aspects of energy metabolism to be studied include glucose metabolism, lipid metabolism, and energy expenditure. For each of these three aspects of energy metabolism, we will measure a primary, secondary, and one or more exploratory outcomes, as follows:

Glucose Metabolism

- **Primary outcome:** Total body insulin sensitivity (measured as glucose disposal rate during a hyperinsulinemic, euglycemic clamp)
- **Secondary outcomes:**
 - Hepatic insulin sensitivity (measured as suppression of endogenous glucose production during a hyperinsulinemic, euglycemic clamp)
 - Fasting plasma glucose
 - Fasting C-peptide
- **Exploratory outcomes:**
 - Insulin-like growth factor binding protein 2 (IGFBP2) and other novel mediators of leptin action on glycemia

Lipid Metabolism

- **Primary outcome:** Rate of lipolysis (measured using stable isotope tracers)
- **Secondary outcomes:**
 - Fasting plasma triglycerides
- **Exploratory outcomes:**
 - Rate of fatty acid turnover (measured using stable isotope tracers)
 - Liver triglyceride (measured using MRI and MRS)
 - Muscle triglyceride (measured using MRS)

Energy Expenditure

- **Primary outcome:** Total 24 hour energy expenditure (measured using indirect calorimetry in the metabolic chamber)
- **Secondary outcomes:**
 - Resting energy expenditure (measured using indirect calorimetry with a hood)

- Skeletal muscle work efficiency (measured as the exercise-induced incremental change in energy expenditure above resting energy expenditure)
- **Exploratory variables:**
 - Spontaneous physical activity (measure using portable accelerometers)
 - Thyroid function
 - Urine and plasma catecholamines
 - Cardiac autonomic nervous system tone (measured using heart rate variability analysis)

Additional outcomes include the following:

Thermal regulation

- Core versus peripheral body temperature
- Thermal comfort (measured using visual analog scales)

Endocrine

- LH pulsatility analysis

Other

- Blood pressure (measured using 24 hour ambulatory monitoring)
- Hunger and satiety (measured using visual analog scales)
- Markers of bone turnover (β -CTX and P1NP) will be measured to look for potential effects of leptin on bone formation and resorption.

Statistical Considerations

Sample Size Justification

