This is an exploratory study of the energy-intake independent effects of leptin initiation and withdrawal in lipodystrophy. Preliminary data are not available to generate estimates of power for each outcome to be tested. The primary comparisons to be tested for each outcome of interest are results at the end of Period 1 versus the end of Period 2, analyzed separately for each group of subjects (leptin-naïve versus leptin treated). Thus, sample size calculations are based on paired, before and after, comparisons within each group of subjects. The data and references used for power calculations are shown in the table, below. Data in the table using the 10% weight loss model are given as percent change from pre-weight loss values, while data from lipodystrophy patients are given as absolute differences between leptin treated and untreated states. All calculations assumed a sample size of 10 and an alpha of 0.05, without correction for multiple comparisons. Because the standard deviations (SDs) of differences between on and off leptin conditions were not reported in publications, the SDs of the difference (used to calculate power for paired comparisons) was estimated in two ways: First, the SDs of differences are calculated by assuming that the SDs of on and off leptin reported in the literature are independent (Power 1 in the table). Second, a “worst-case scenario” was assumed that the SDs on and off leptin in the literature are perfectly positively correlated (Power 2 in the table). The first scenario is the commonly used method, while the second case is the most conservative calculation.

Outcome	Model	Duration of leptin	Off-leptin mean (SD)	On-leptin mean (SD)	Power 1	Power 2
Total energy expenditure ¹¹ (% Δ in kcal/day)	10% wt loss	5 wk	-22% (15.8)	-6% (4.7)	0.92	0.79
Skeletal muscle work efficiency ¹¹ (% Δ in kcal/min expended during exercise vs. at rest)	10% wt loss	5 wk	20% (12.6)	3% (2.5)	0.99	0.97
Resting energy expenditure ²⁴	lipodystrophy	4 mo	35.5 (8.2)	33.6 (6.7)	0.14	0.11
T3 ¹¹ (% Δ)	10% wt loss	5 wk	-9% (6.3)	3% (3.2)	0.99	0.99

T3 ⁴³ (nmol/L)	lipodystrophy	4 mo	124 (37)	114 (26)	0.18	0.13
T4 ¹¹ (% Δ)	10% wt loss	5 wk	-7% (7.9)	-1% (1.3)	0.77	0.66
fT4 ⁴³ (pmol/L)	lipodystrophy	4 mo	1.05 (0.15)	1.03 (0.15)	0.09	0.08
TSH ⁴³ (μU/mL)	lipodystrophy	4 mo	1.37 (0.37)	1.24 (1.1)	0.10	0.09
Norepinephrine ¹¹ (% Δ)	10% wt loss	5 wk	-12% (15.8)	-7% (12.6)	0.19	0.14
Epinephrine ¹¹ (% Δ)	10% wt loss	5 wk	-40% (35)	28% (47)	0.98	0.83

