Sympathetic nervous system tone ¹¹ (% Δ in mean ECG R-R interval after atropine + esmolol vs. atropine alone)	10% wt loss	5 wk	-25% (22.1)	1% (1.6)	0.98	0.97
Liver volume ²⁴ (cm ³)	lipodystrophy	4 mo	3055 (1051)	2433 (763)	0.45	0.29
Total body insulin sensitivity ³¹ (glucose infusion rate during clamp, mg*kg ⁻¹ *min ⁻¹)	lipodystrophy	1 mo	2.5 (0.79)	3.7 (1.1)	0.87	0.63
Total body insulin sensitivity ²⁵ (glucose infusion rate during clamp, mg*kg ⁻¹ *min ⁻¹)	lipodystrophy	4 mo	1.2 (0.35)	5.4 (1.6)	1	1
Hepatic insulin sensitivity ²⁵ (% suppression of endogenous glucose production during clamp)	lipodystrophy	4 mo	40 (10.4)	82 (8.7)	1	1
Fasting glucose ³¹ (mg/dL)	lipodystrophy	7 d	172 (20)	120 (12)	1	0.99
Fasting triglycerides ³¹ (mg/dL)	lipodystrophy	7 d	700 (272)	260 (98)	0.99	0.98
Fasting triglycerides ³¹ (mg/dL)	lipodystrophy	14 d	700 (272)	110 (38)	1	0.99
Rate of lipolysis ²⁵ (glycerol turnover, μmol*kg fat mass ⁻¹ *min ⁻¹)	lipodystrophy	4 mo	78 (36)	25 (7)	0.99	0.99

Based on these calculations, a sample size of 10 subjects in each group (leptin-naïve and leptin-treated) will provide greater than 80% power (in most cases greater than 95%) for the following primary and secondary outcomes:

Glucose Metabolism

1. Total body insulin sensitivity
2. Hepatic insulin sensitivity
3. Fasting plasma glucose

Lipid Metabolism

1. Rate of lipolysis
2. Fasting triglycerides

Energy Expenditure

1. Total energy expenditure
2. Skeletal muscle work efficiency

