Exploratory outcomes for which we anticipate greater than 80% power include epinephrine and sympathetic nervous system tone. Discrepant data exist for the effects of leptin on thyroid function (specifically, T3) based on the model used (lipodystrophy versus 10% weight loss), and this study should help to clarify whether this effect does or does not exist in lipodystrophy. We do not anticipate observing significant changes in resting energy expenditure; however, because this procedure is minimal risk, we feel that it will be important to document negative results for this outcome. Certain outcome measures, such as liver triglyceride (for which liver size was a proxy in the table, above), and insulin sensitivity, appear to progressively change over time with leptin replacement. For these outcomes, a 2 week intervention may be insufficient to observe statistically significant results. For other outcome measures, such as intramyocellular triglyceride, preliminary data on the short-term effects of leptin are not available, but effects, if present, are unlikely to be detectable by two weeks.

Therefore, in addition to obtaining data after 2 weeks of leptin withdrawal or initiation, we will restudy subjects in the leptin-naïve group 6 months (range is 5-9 months) after leptin initiation to look for changes that may not be detectable by 2 weeks.

Because some subjects may not complete the study, or may not have interpretable data for each outcome, we plan to enroll up to 20 subjects in each group in order to have 10 completers per group.

Statistical Methods for Data Analysis

Data will be analyzed separately for the leptin naïve and leptin treated subjects. This is done because the effects of leptin withdrawal after long-term treatment are likely to be different from the effects of leptin initiation after long-term deficiency.

Analysis of Primary Outcomes

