focused on the 48 hours immediately before and after leptin initiation and withdrawal. An additional 48 hours of monitoring will be performed at the end of Period 2, and during the long-term follow-up visit for subjects in the leptin-naïve group, to look for longer term effects.

6. Heart rate variability: Heart rate will be measured and recorded using a portable ECG Holter monitor, which will be downloaded and analyzed for heart-rate variability using power spectrum analyses. Testing will be performed in conjunction with blood pressure monitoring.
7. Visual Analog Scales (hunger, thermal regulation): Patients will be given a questionnaire to determine their level of thermal comfort and hunger using visual analog scales (VAS), as shown in Appendix III. The hunger VAS question has been characterized previously, and is digitized exactly onto an iPad app⁴⁴. Testing does not require supervision, and will be performed on a daily basis after lunch.
8. Skin temperature: Wireless probes (iButtons, Maxim Inc., Sunnyvale, CA) will record skin temperature with data reported each minute. The positions of the skin sensors at five sites (deltoid, hand, pectoralis major, anterior thigh, and shin) will be according to the ISO standards⁴⁵. Skin temperature monitoring will be performed prior to, during, and for one hour following each exercise test, as well as throughout each stay in the metabolic chamber.

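### The claim of over 80% power for sympathetic tone rests on a drug-blockade test that this trial does not perform; the power for its heart rate variability outcome is unknown

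*Combined protocol and SAP*

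**What the plan says.** The paragraph after the power results in Sample Size Justification says: "Exploratory outcomes for which we anticipate greater than 80% power include epinephrine and sympathetic nervous system tone".

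The power table has one row for sympathetic nervous system tone. It defines the measure as the percent change in "mean ECG R-R interval after atropine + esmolol vs. atropine alone". The row comes from the 10% weight-loss model after 5 weeks of leptin, with off-leptin mean -25% (SD 22.1), on-leptin mean 1% (SD 1.6), Power 1 of 0.98 and Power 2 of 0.97. On the scale of such rows the section explains: "Data in the table using the 10% weight loss model are given as percent change from pre-weight loss values". On the calculation it says: "All calculations assumed a sample size of 10 and an alpha of 0.05, without correction for multiple comparisons", and that "sample size calculations are based on paired, before and after, comparisons within each group of subjects".

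The trial's own outcome is listed under Outcome Measures, Energy Expenditure, among the exploratory variables: "Cardiac autonomic nervous system tone (measured using heart rate variability analysis". Metabolic Testing, item 6, describes the procedure as a portable Holter ECG recording, "which will be downloaded and analyzed for heart-rate variability using power spectrum analyses", done together with blood pressure monitoring. The schedule table in Study Procedures lists only heart rate monitoring.

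**The concern.** Power belongs to a particular variable, through its expected change and the SD of that change. The table row describes how far the R-R interval shifts when esmolol is added to atropine, which isolates sympathetic drive pharmacologically. A spectral index from a Holter recording without blockade is another quantity, on another scale, with another variance. Using one general label for both carries the power figure from the first to the second without support.

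What is at stake is the reading of a null result. If heart rate variability does not change with leptin, a stated power above 80% invites the conclusion that a real effect would probably have been seen. The design has not been shown to support that conclusion.

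**Working it through.** **Is a blockade test part of this trial?** Atropine and esmolol appear in the power table row and nowhere else in the text available: not in Outcome Measures, the schedule, Metabolic Testing, Endocrine Evaluation, or the procedure risks that could be read. Part of the risks section was not available for checking, but a test absent from the outcome list, the schedule and the procedure descriptions is not a planned measurement.

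**Reproducing the printed power.** Inputs are from the table row, with n = 10 pairs and alpha 0.05; sidedness is not stated.

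- Mean difference: 1 - (-25) = 26.
- SD of the difference, on and off values independent (Power 1): √(22.1² + 1.6²) = √490.97 = 22.16.
- SD of the difference for Power 2: the printed value fits the sum of the SDs, 22.1 + 1.6 = 23.7.
- One-sided normal approximation: power = Φ(26/SD × √10 - 1.645).
  - SD 22.16: Φ(3.711 - 1.645) = Φ(2.066) = 0.981, printed as 0.98.
  - SD 23.7: Φ(3.469 - 1.645) = Φ(1.824) = 0.966, printed as 0.97.

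The same inputs under other test conventions give:

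| Method | SD 22.16 | SD 23.7 |
|---|---|---|
| One-sided z | 0.981 | 0.966 |
| Two-sided z | 0.960 | 0.934 |
| One-sided paired t (9 df) | 0.961 | 0.939 |
| Two-sided paired t (9 df) | 0.909 | 0.869 |

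Analysis of Primary Outcomes plans a paired t-test or Wilcoxon test for any significant difference, with similar methods for the other outcomes. The two-sided paired t value, 0.909 for a standardised effect of 26/22.16 = 1.17, is therefore the nearer match to the plan. Every variant exceeds 80%, so this does not decide the point.

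**What can be said about heart rate variability.** The documents give no mean, SD or effect size for any spectral index, so its power cannot be computed. What can be computed is the standardised paired effect (mean difference divided by SD of differences) needed for 80% power at n = 10:

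- One-sided z: (1.645 + 0.842)/√10 = 0.79.
- One-sided paired t: 0.85.
- Two-sided paired t: 1.00.

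Power at n = 10 over a range of **assumed** effects, for illustration only:

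| Assumed standardised effect | Two-sided paired t | One-sided z |
|---|---|---|
| 0.3 | 0.134 | 0.243 |
| 0.5 | 0.293 | 0.475 |
| 0.8 | 0.616 | 0.812 |
| 1.0 | 0.803 | 0.935 |

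Depending on the unknown effect, power could fall on either side of 80%.

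**The case against.** The strongest case for the plan is that it already hedges. The study calls itself exploratory, the outcome is listed as exploratory, and Sample Size Justification admits that preliminary data do not exist for every outcome. The table row names the blockade method, the weight-loss model and the five-week duration, so a careful reader can see that the input comes from elsewhere. The printed figures are reproducible, and the blockade row passes 80% under every convention tried. No decision rule depends on heart rate variability, and the sample size of 10 does not depend on this row.

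Much of this stands, and it limits the severity. It does not remove the mismatch. The general caveat about missing preliminary data describes exactly the position of heart rate variability, yet the later sentence makes a positive power claim under the sympathetic tone label. The same paragraph says openly that liver size stood in for liver triglyceride; no such label is given here. The row names the source's method but does not say that the trial uses a different one. That the calculation can be reproduced does not help when its inputs describe another measurement.

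**Conclusion.** The concern holds. The stated power of 0.97 to 0.98 is unsupported for the outcome this trial measures. The power for heart rate variability is unknown; it has not been shown to be below 80%. This rests on the documents giving no effect size or SD for a spectral index and describing no blockade procedure. The figure of 0.91 for the blockade measure assumes a two-sided paired t-test and independent on- and off-leptin values; it is a side point, since the row stays above 80%.

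The row also differs from the trial in population (weight-reduced healthy subjects rather than people with lipodystrophy) and in duration (5 weeks rather than 14 days). Those differences are visible in the table and are not the basis of this point. The epinephrine half of the sentence does not share the mismatch, because catecholamines are measured in the trial. The effect is confined to how an exploratory result would be read, so this is a minor correction.

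**What to change.** In Sample Size Justification:

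1. Remove sympathetic nervous system tone from the sentence listing exploratory outcomes with more than 80% power.
2. Mark its table row as a pharmacological-blockade measure that this trial does not perform, as the section already does in text for liver size.
3. State that no power estimate is available for heart rate variability, and that a null result for it should not be taken as evidence of no effect on the strength of the power table.

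The cost is wording only. Design, sample size, procedures and analyses are unchanged; one stated figure becomes less favourable.

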Measurements in each of the primary outcomes will be analyzed using the paired t-test (for normally distributed variables) or Wilcoxon paired test (for skewed variables) to test if there is any significant difference between the two study periods (on and off leptin) for each group (leptin naïve and leptin treated), respectively. In addition, mixed models incorporating baseline (pre-diet) parameters as covariates will be used to adjust for any effects of the inpatient, metabolic diet, independent of leptin's effects. For variables with more than 2 measurements during Period 2, repeated measure linear models (Mixed model or GLM) will be used to study the time effect, using pooled data from the 2 periods. Potential covariates to be explored in the model include: Age, sex, race, percent body fat, lean mass, body weight, type of lipodystrophy, and endogenous leptin level. To account for any deviation from the isocaloric protocol diet, actual caloric intake will be included as a covariate in mixed model analyses.

Additional correlations between variables within and between each of the major outcome categories (glucose metabolism, lipid metabolism, and energy expenditure) will be analyzed using either Pearson's correlation or simple linear regressions. These include the following:

1. Association between change in total body insulin sensitivity and changes in hepatic insulin sensitivity, fasting plasma glucose, and C-peptide
2. Association between change in rate of lipolysis, and changes in fasting triglycerides and fatty acid turnover
3. Association between insulin sensitivity and ectopic lipid stores, and rates of lipolysis and fatty acid turnover
4. Association between change in total energy expenditure and changes in resting energy expenditure, skeletal muscle work efficiency, spontaneous physical activity, thyroid function, catecholamines, and cardiac autonomic nervous system tone.

Analysis of Secondary and Exploratory Outcomes

Methods for analysis of secondary outcomes will be similar to those for primary outcomes. In addition, we will perform analysis to study the following associations between categories of outcome measures:

1. Association between the Ectopic Lipid measurements with Glucose and Lipid measurements
2. Association between the Endocrine measurements with Energy Expenditure measurements

Analysis of long-term data

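### Resting energy expenditure is to be documented as negative at a tabulated power of 0.14/0.11, with no interval or margin that could make a non-significant result negative; T3 has a milder form of the problem

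*Combined protocol and SAP*

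**What the plan says.** The Sample Size Justification rests on within-group comparisons of the end of Period 1 with the end of Period 2: "sample size calculations are based on paired, before and after, comparisons within each group of subjects". It adds: "All calculations assumed a sample size of 10 and an alpha of 0.05, without correction for multiple comparisons". The power table gives:

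- REE, lipodystrophy, 4 months of leptin: 35.5 (8.2) off, 33.6 (6.7) on, power 0.14/0.11.
- T3, lipodystrophy, 4 months: 124 (37) off, 114 (26) on, power 0.18/0.13.
- T3, 10% weight-loss model, 5 weeks: -9% (6.3) off, 3% (3.2) on, power 0.99/0.99.

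The text after the table says no significant REE change is anticipated, but that the test carries minimal risk and "we feel that it will be important to document negative results for this outcome". On T3 it notes that the two models disagree and says "this study should help to clarify whether this effect does or does not exist in lipodystrophy".

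Under Outcome Measures, REE is a secondary outcome and thyroid function an exploratory one. Under Statistical Methods for Data Analysis, the primary outcomes get paired t or Wilcoxon tests, mixed models with pre-diet baseline and caloric intake as covariates, and repeated-measures models where Period 2 has more than two measurements. Secondary outcomes are handled similarly. No equivalence margin, smallest difference of interest or confidence-interval rule is given for any outcome.

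**The concern.** A test with 11-14% power at the tabulated difference will usually be non-significant if that difference is real, and will usually be non-significant if there is no effect. The p-value then hardly separates the two cases. To document a negative, one has to show which effects the data rule out, and the plan sets no way to do that.

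Energy expenditure is one of the three parts of the primary aim, and the Introduction describes the human evidence on it as limited. A published negative for REE in this rare disease could carry weight that the design cannot support. For T3, the plan hopes to learn whether an effect does or does not exist, and the second half of that question needs the same kind of rule.

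**Working it through.** **Inputs.** n = 10 pairs, alpha 0.05, and the means and SDs above, all from the Sample Size Justification. The on/off correlation r is not given, so r = 0, 0.8 and 0.9 are shown as assumptions. The REE row gives no unit, so results are also expressed as a percentage of the off-leptin mean.

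**1. Reproducing the plan's power.** Sidedness is not stated. The figures are recovered to within 0.01 by a one-sided normal approximation, power = Φ(d·√10/SD_diff − 1.645).

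- REE, independent: SD_diff = √(8.2² + 6.7²) = 10.59; 1.9 × 3.162/10.59 = 0.567; Φ(−1.078) = 0.141 (table 0.14).
- REE, second column: SD_diff = 8.2 + 6.7 = 14.9; Φ(0.403 − 1.645) = 0.107 (table 0.11).
- T3 lipodystrophy, independent: SD_diff = √(37² + 26²) = 45.22; Φ(0.699 − 1.645) = 0.172 (table 0.18).
- T3 lipodystrophy, second column: SD_diff = 63; Φ(0.502 − 1.645) = 0.127 (table 0.13).

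The second column needs the SDs added, which corresponds to perfect negative correlation, although the text calls it positive. That is a separate matter.

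**2. Power of a two-sided paired t-test** (noncentral t, 9 df). REE: 0.080 and 0.065 for the two SD assumptions. T3 lipodystrophy: 0.096 and 0.074. At r = 0.8 and 0.9, REE has 0.19 and 0.32, and T3 has 0.24 and 0.36.

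**3. What the interval can exclude.** Half-width = t(0.975, 9) × SD_diff/√10 = 2.262 × SD_diff/3.162, with SD_diff = √(SD_off² + SD_on² − 2r·SD_off·SD_on).

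| | r = 0 | r = 0.8 | r = 0.9 |
|---|---|---|---|
| REE SD_diff | 10.59 | 4.92 | 3.64 |
| REE half-width (% of 35.5) | 7.6 (21%) | 3.5 (10%) | 2.6 (7%) |
| T3 SD_diff | 45.2 | 22.5 | 17.7 |
| T3 half-width (% of 124) | 32.3 (26%) | 16.1 (13%) | 12.7 (10%) |

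The tabulated REE difference is 1.9/35.5 = 5.4%. With an observed change of exactly zero, excluding it needs SD_diff below 1.9 × 3.162/2.262 = 2.66, that is r above (112.13 − 2.66²)/109.88 ≈ 0.96, where 112.13 = 8.2² + 6.7² and 109.88 = 2 × 8.2 × 6.7.

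**4. The two T3 rows.** The weight-loss figures are percentages of the pre-weight-loss value: 91 off leptin, 103 on leptin. The rise is 12/91 = 13.2% of the off-leptin value, or 16.4 on a mean of 124 if it carries over as a percentage. The lipodystrophy row is a fall of 10/124 = 8.1%. The two effects have opposite signs. The 0.99 power uses SDs from weight-reduced healthy subjects. With the lipodystrophy SDs, two-sided power for a change of 16.4 is 0.18 (independent) or 0.11 (summed SDs). It rises to 0.54 at r = 0.8 and 0.74 at r = 0.9.

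**The case against.** The plan is candid. It calls itself exploratory, prints the low power, leaves REE and T3 off its lists of well-powered outcomes, and says it expects no significant REE change. Documenting negative results can be read simply as a promise to report a non-significant secondary outcome. Four stronger readings are tempting and are not supported:

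- **That the paired test is the only inference.** Mixed and repeated-measures models are also planned. REE is measured on admission, at the end of Period 1 and about every four days in Period 2, so the model-based interval may be narrower than the simple paired one above.
- **That the trial claims to settle the T3 question, or will report p>0.05 as no effect.** The text says only that it should help to clarify, and nowhere states such a rule.
- **That the table shows only low power for T3.** It has a second row at 0.99/0.99, and the T3 sentence is about the disagreement between the two rows.
- **That at r = 0.8 or below an observed T3 change of zero cannot exclude the weight-loss effect.** On the off-leptin base the effect is 13.2% and the half-width at r = 0.8 is 12.97%, so it is just excluded there. Non-exclusion holds only below about r = 0.79. If the study saw the lipodystrophy row's own 8% fall, the paired CI would exclude the rise once r passed about 0.36: 10 + 16.35 = 26.35; 26.35 × 3.162/2.262 = 36.8; (2045 − 36.8²)/1924 ≈ 0.36, where 2045 = 37² + 26² and 1924 = 2 × 37 × 26.

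These points soften the T3 half and limit what can be said about how results will be reported. None supplies a criterion for a negative REE result.

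**Conclusion.** The concern holds for REE. Followed as written, the plan could support a negative conclusion that 10 completers cannot deliver: tabulated power is 0.14/0.11, and the simple paired 95% CI reaches 21%, 10% or 7% of the off-leptin mean at r = 0, 0.8 or 0.9, against a tabulated difference of about 5%. This assumes that the literature SDs apply, although they come from 4 months of leptin rather than 14 days, and that r lies in the range shown. The planned models may improve precision by an amount the documents do not let one calculate, but they too lack a rule for a negative.

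For T3 the weakness is the same in kind and milder: the outcome is exploratory, the wording is modest, and the design may tell a rise from a fall. It is unlikely to show that no effect exists. Excluding the lipodystrophy row's fall after an observed zero would need r of about 0.96: 10 × 3.162/2.262 = 13.98; (2045 − 13.98²)/1924 ≈ 0.96.

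This should be changed, but it does not affect the primary outcomes or the sample size.

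**What to change.** For REE and T3, state that the within-group mean change will be reported with its 95% CI, from the paired comparison and from the planned mixed model, and that p>0.05 will not be described as negative.

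- **REE:** name a smallest difference of interest before analysis. Call the result negative only if the CI excludes it, and otherwise inconclusive.
- **T3:** do not use a symmetric 12-point margin, because the lipodystrophy row's 8% fall would lie inside it and could be declared negative. State separately whether the CI excludes the weight-loss row's rise (12 points of the pre-weight-loss value, about 13% of off-leptin) and the lipodystrophy row's fall (about 8%). If it excludes neither, call the result inconclusive.

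The cost is a few sentences and one REE difference to be justified, with no extra subjects or tests. The downside is that the likely conclusion becomes inconclusive rather than negative.
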